Following the Response Evaluation Period, all patients will enter the Follow-Up Period from Week 37 through Week 96. Visits will occur at Weeks 48, 72, and 96/EOS. Patients will be assessed for response and offered retreatment if they relapse after Week 48. Patients who relapse will be given weekly IV treatment for an additional 12 weeks according to the patient's randomized treatment assignment. Once a patient receives retreatment for relapse in the Follow-Up period, the patient will not be given additional retreatment for relapse. As Week 96 is the end-of-study visit, no relapse retreatment will be offered at that time.

Between visits, interim telephone contacts with patients will occur at Weeks 40, 44, 60, and 84 to monitor patient safety. Telephone contacts may be skipped if they overlap with a relapse retreatment visit.

CONFIDENTIAL

No use, disclosure, or reproduction outside of Omersus without prior written authorization

All patients will continue optimized antihypertensive medication treatment and attempt to maintain optimized blood pressure throughout the study.

Rescue Therapy: A patient may be considered for rescue therapy (which may include corticosteroids or immunosuppressants) by the Investigator according to local practice if all the following conditions are met:

- It is recommended that the patient be in the study for over one year. However, rescue therapy may be administered if the patient has been in the study for less than one year, if clinically warranted
- Patient meets study eligibility criteria (other than eGFR ≥ 30), including 24-hour UPE > 1 g or 24-hour uPCR > 0.75 , twice over an 8-week period
- Patient has 100% increase in 24-hour UPE from baseline and patient has a 30% decrease in eGFR from baseline, as measured twice over an 8-week period

The Investigator is strongly encouraged to contact the Medical Monitor to discuss the use of rescue therapy.

Rescue therapy for study patients is not encouraged given that there is very limited or no specific medication or treatment regimen approved for IgAN. However, if the Investigator feels that rescue therapy is required after discussing the case with the Medical Monitor, and the patient meets the above criteria, the patient may be managed per local practice at the Investigator's discretion. Patients requiring rescue therapy will be discontinued from study treatment and will continue to be followed in the study.

Open-Label Option for a Sub-Group of the High-Risk Proteinuria Group

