The analysis of the key secondary efficacy eGFR endpoints (i) the rate of change in eGFR over 2 years in the high-risk proteinuria group and (ii) the rate of change in eGFR over 2 years in all patients will be performed only if the primary UPE efficacy endpoint in the ≥ 2 g/day population is significant at 5% level of significance in a 2-sided test. If the

CONFIDENTIAL

No use, disclosure, or reproduction outside of Omersus without prior written authorization

primary endpoint is met, then key secondary endpoints (i) and (ii) will be sequentially tested at 5% level of significance in a 2-sided test respectively.

The key secondary rate of change in eGFR over 2 years in the high-risk proteinuria group and the all-patients population will be analyzed by a random coefficients model for the FAS population. This analysis will be performed after the final database lock.

Safety Analyses

The safety endpoints will be summarized descriptively by treatment group. Patient incidence of treatment-emergent adverse events (TEAEs), treatment-related AEs, treatment-emergent serious AEs, TEAEs leading to study treatment discontinuation and TEAEs leading to death, as well as maximum severity of TEAEs will be summarized by Medical Dictionary for Regulatory Activities System Organ Class and Preferred Term.

Laboratory tests, including ECG and vital signs, will be descriptively summarized by treatment group and visit.

Pharmacokinetic, Pharmacodynamic, and Biomarker Analyses

By sparse sampling, blood will be collected from patients at intervals to enable population pharmacokinetic (PK) analyses. Biomarker, ADA, NAb, and pharmacodynamic (PD) data will be summarized. An exploratory evaluation of other relevant biomarkers may be conducted.

CONFIDENTIAL

No use, disclosure, or reproduction outside of Omertos without prior written authorization

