8.3.1. Early Discontinuation of Study Drug

A patient must permanently discontinue study drug under any of the following circumstances:

- The patient becomes pregnant. Study drug must be discontinued immediately, and the pregnancy reported to the Sponsor.
- The patient wishes to discontinue study drug treatment for any reason.
- The patient experiences a medical emergency that necessitates discontinuing study drug treatment.
- The Investigator, Sponsor, or patient's primary care provider decides to discontinue treatment for medical reasons other than nonresponse to study treatment, or due to the patient's significant noncompliance with the protocol.

The reason for termination of study drug before study completion must be recorded in the patient's case report form (CRF). The patient should complete all scheduled study visits provided

CONFIDENTIAL

No use, disclosure, or reproduction outside of Omeros without prior written authorization

written consent to do so has not been withdrawn. Patients who discontinue study drug prematurely will not be replaced.

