10.2.9. Early Termination

Reasons that patients may discontinue study treatment or withdraw from study participation are detailed in Sections [8.3.1](#) and [8.3.2](#), respectively.

Patients will be encouraged to complete all evaluations. However, provided written consent to do so has not been withdrawn, patients who prematurely discontinue study drug treatment should complete all scheduled study visits, and patients who prematurely discontinue study participation should complete the evaluations scheduled for the FU3/EOS (Week 96) visit. Patients with ongoing SAEs at the time of early termination from the study should be followed for resolution (as possible) or Investigator confirmation that the event is believed to be stable.

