14.1.12.2. Adverse Events

The incidence of all reported AEs and treatment-related AEs before the initiation of the open-label treatment of narsoplimab will be tabulated by treatment group. AE data collected during the

CONFIDENTIAL

No use, disclosure, or reproduction outside of Omeros without prior written authorization

open-label period will be summarized separately. AEs will be classified by System Organ Class (SOC) and Preferred Term (PT) using the Medical Dictionary for Regulatory Activities (MedDRA).

The focus of AE summarization for this study will be on treatment-emergent AEs (TEAEs). A TEAE is defined as an event that first occurs or worsens in severity after the first dose of study drug.

AEs will be listed and summarized by treatment group, MedDRA PT, severity, and relationship to study drug. In the event of multiple occurrences of the same AE with the same PT in one patient, the AE will be counted once as the worst occurrence. The incidence of AEs will be tabulated by SOC and treatment group. AEs leading to premature discontinuation of study drug or withdrawal from the study will be summarized and listed in the same manner.

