### **3.4.1. Adverse Events**

Treatment-emergent adverse events (TEAEs) are defined as follows:

- During the blinded treatment period, an AE is treatment-emergent if it occurs or worsens in severity from pre-treatment after the first dose of study drug but before the first dose of narsoplimab in the open-label treatment period (blinded TEAE)
- During the open-label treatment period, an AE is treatment-emergent if it occurs or worsens in severity from the end of the blinded treatment period after the first dose of narsoplimab in the open-label treatment period (open-label TEAE)

All AEs will be classified by system organ class and preferred term using the Medical Dictionary for Regulatory Activities (MedDRA). An AE is considered treatment-related if the relationship to study drug is either probable or possible as assessed by the investigator.

Patient incidence by treatment group of the following AEs will be provided:

- Pre-treatment AEs (AEs that occurred prior to the start of study drug) by MedDRA system organ class (SOC), preferred term, and treatment group
- Blinded treatment period:

- TEAEs by MedDRA SOC, preferred term, and treatment group
- TEAEs by MedDRA preferred term and treatment group
- TEAEs that are treatment-related by MedDRA SOC, preferred term, and treatment group
- TEAEs by MedDRA preferred term, maximum severity, and treatment group
- TEAEs leading to study discontinuation by MedDRA SOC, preferred term, and treatment group
- TEAEs that are serious by MedDRA SOC, preferred term, and treatment group
- TEAEs that are treatment-related and serious by MedDRA SOC, preferred term, and treatment group
- TEAEs leading to death by MedDRA SOC, preferred term, and treatment group
- Open-label treatment period:
  - Open-label TEAEs by MedDRA SOC, preferred term, and treatment group
  - Open-label TEAEs by MedDRA preferred term and treatment group
  - Open-label TEAEs that are treatment-related by MedDRA SOC, preferred term, and treatment group
  - Open-label TEAEs by MedDRA preferred term, maximum severity, and treatment group
  - Open-label TEAEs leading to study discontinuation by MedDRA SOC, preferred term, and treatment group
  - Open-label TEAEs that are serious by MedDRA SOC, preferred term, and treatment group
  - Open-label TEAEs that are treatment-related and serious by MedDRA SOC, preferred term, and treatment group
  - Open-label TEAEs leading to death by MedDRA SOC, preferred term, and treatment group

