- Blinded and open-label treatment periods combined for patients who receive narsoplimab only. TEAEs are determined relative to the first dose of narsoplimab
  - TEAEs by MedDRA SOC and preferred term
  - TEAEs by MedDRA preferred term
  - TEAEs that are treatment related by MedDRA SOC and preferred term
  - TEAEs by MedDRA preferred term and maximum severity
  - TEAEs leading to study discontinuation by MedDRA SOC and preferred term
  - TEAEs that are serious by MedDRA SOC and preferred term

- TEAEs that are treatment-related and serious by MedDRA SOC and preferred term
- TEAEs leading to death by MedDRA SOC and preferred term

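### The SAP's adverse-event tables cover discontinuation of the study but omit the protocol's summary of events leading to discontinuation of study drug

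*SAP*

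**What the plan says.** SAP section 3.4.1 itemises the incidence tables in three blocks. The discontinuation entries are:

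- blinded period: "TEAEs leading to study discontinuation by MedDRA SOC, preferred term, and treatment group"
- open-label period: "Open-label TEAEs leading to study discontinuation by MedDRA SOC, preferred term, and treatment group"
- blinded and open-label periods combined, narsoplimab recipients only: "TEAEs leading to study discontinuation by MedDRA SOC and preferred term"

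None of the blocks has an entry for stopping study drug, and the section does not define study discontinuation.

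The protocol describes this summary twice. Under Safety Analyses, the synopsis includes "TEAEs leading to study treatment discontinuation and TEAEs leading to death" among the incidences to be given by system organ class and preferred term. Section 14.1.12.2 says that "AEs leading to premature discontinuation of study drug or withdrawal from the study will be summarized and listed in the same manner", which refers back to summaries by preferred term, system organ class and treatment group.

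The protocol defines the two events separately. Section 8.3.1 governs stopping drug and section 8.3.2 governs leaving the study. Section 10.2.9 adds that, unless consent is withdrawn, "patients who prematurely discontinue study drug treatment should complete all scheduled study visits". The same holds after rescue: "Patients requiring rescue therapy will be discontinued from study treatment and will continue to be followed in the study".

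**The concern.** Stopping drug and leaving the study are often nearly the same event, and loose wording then does little harm. In this trial they are kept apart on purpose. Initial dosing lasts 12 weeks and follow-up runs to Week 96, so a patient can stop infusions early for an adverse event and still complete the study. That patient belongs in the protocol's summary but not in the SAP's table.

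At stake is the tabulation that shows which events made the drug intolerable, and in which arm. Safety and tolerability is a stated secondary objective (protocol section 6.2). SAP section 2.9.5 also schedules safety analyses at the interim analysis of the UPE endpoint, when the data may support a regulatory filing, so the gap would first appear there.

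**Working it through.** No sample size, power or error rate is involved, so the check compares the texts and then the sets of events that they define.

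**Step 1: which events each text covers.** Let D be the adverse events that lead to stopping study drug, and W those that lead to leaving the study.

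| Source | Planned summary |
|---|---|
| Protocol synopsis, Safety Analyses | D |
| Protocol 14.1.12.2 | D or W |
| SAP 3.4.1, each of three blocks | W |

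**Step 2: whether study discontinuation could be shorthand for stopping drug.** The SAP does not support that reading. For disposition, its section 3.2.1 names patients who stopped drug early and patients who withdrew from the study as two groups. The treatment-policy estimands in SAP Table 1 depend on the same separation, since they follow patients for the endpoint whether or not randomised treatment has stopped. SAP section 4, which records protocol and SAP changes, neither mentions nor justifies dropping the drug-discontinuation summary.

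**Step 3: the direction of the gap.** Against section 14.1.12.2, the events missed are those in D but not in W. A patient withdrawn under section 8.3.2 also stops drug, whereas a patient who stops drug under section 8.3.1 does not thereby leave the study. The SAP table can therefore equal or fall short of the protocol's combined set, but cannot exceed it. W is not simply a smaller version of D, because a patient who leaves the study because of an event after completing a course of dosing is in W only. This is why section 14.1.12.2 asks for both.

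**Step 4: the size of the gap.** Among patients whose drug is stopped for an adverse event, the share missing from the SAP's discontinuation table is the share who remain in the study. It can lie anywhere from none to all. The documents give neither this share nor the rate of such stops, so no number follows.

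**Step 5: where the missed events still appear.** Each remains in the SAP 3.4.1 tables by system organ class and preferred term, by preferred term, and by maximum severity. It also appears in the treatment-related and serious tables where it qualifies. The patient's drug stop is summarised and listed with its reason under SAP 3.2.1. Neither output links the two: the event tables do not mark which events stopped drug, and no breakdown by system organ class or preferred term is specified for the disposition summary.

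**The case against.** The strongest reply is that little is lost. The events are counted in the overall tables. Disposition reports drug stops with reasons, and if adverse event is one of the reason categories (the documents do not list them), the number of such stops per arm will be available whatever section 3.4.1 says. The protocol's commitment in section 14.1.12.2 has not been withdrawn. All safety analyses are descriptive (SAP section 2.9.4), so nothing here affects type I error, power or the estimands. The data are recorded, so the table can be produced at any time.

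Most of that stands, and it limits the point. It does not close the gap, because a count of stops by reason is not a breakdown by event, and that breakdown is what the protocol planned.

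The reply also disposes of some stronger readings. A reader might infer that the SAP has replaced the protocol's safety endpoint. It has not: the endpoint in protocol section 7.2.4 is general safety and tolerability, and this is one planned summary under it. A reader might infer that most drug-stopping events would go unreported. They would be reported, though not identified as drug-stopping, and the word most needs a retention rate that the documents do not give. Nor do the documents show that the omission favours either arm. Finally, the existing SAP line is not an error to be replaced, since section 14.1.12.2 asks for study withdrawal as well.

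**Conclusion.** The point holds as an incomplete table list. SAP section 3.4.1 omits, in all three blocks, a summary that the protocol plans in two places, and the trial's follow-up rules make the omitted summary different from the one listed. Drug-stopping events in retained patients would be absent from the discontinuation tables, and no output specified in the SAP would show by system organ class, preferred term and arm which events stopped treatment. The direction is settled: the tables can match or understate the protocol's combined set. The size cannot be stated.

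The conclusion assumes that the tables are programmed from the SAP wording as it stands, and that study discontinuation carries the meaning that SAP 3.2.1 gives to study withdrawal. If the sponsor meant stopping drug, the wording still needs correcting, and the study-withdrawal summary is then the one missing. Efficacy inference is unaffected. The correction should be made before the interim safety tables are produced.

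**What to change.** In SAP section 3.4.1, make two changes in each of the blinded, open-label and combined narsoplimab blocks:

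- add a line for *TEAEs leading to discontinuation of study drug*, with the same system organ class, preferred term and (where the block uses it) treatment-group layout as the other tables;
- keep the existing line, reworded as *TEAEs leading to withdrawal from the study*.

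Together these match protocol section 14.1.12.2 and supply the summary named in the synopsis.

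The cost is a wording change and one extra table per block. No new data are needed: protocol sections 8.3.1 and 8.3.2 require the reason for stopping drug and for withdrawal to be recorded in the CRF, and section 12.3.1 requires the action taken for each adverse event. Trial conduct, sample size and alpha do not change.

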### **3.4.2. Clinical Laboratory Tests**

Summary statistics for the actual values and the change from baseline will be tabulated for laboratory results by treatment period (blinded and open-label), treatment group and scheduled visit. Patients with laboratory values outside of the normal reference range at any post-baseline assessment will be listed by treatment period and treatment cohort. Shift tables comparing the baseline NCI CTCAE grade to the worst post-baseline grade will be provided by treatment period and treatment group.

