10.1.9. Laboratory Assessments

The central laboratory will be responsible for comprehensive metabolic panel (CMP), complete blood count with differential (CBC+diff), hemoglobin A1c (HgbA1c), urinalysis (UA), uPCR, uACR, 24-hour UPE, viral serology, and serum pregnancy testing per Table 2. Other tests listed in Table 2 will be performed by the Sponsor or a designated laboratory.

Specific instructions for processing, labeling, and shipping samples will be provided in the central laboratory manual. The date and time of sample collection will be reported to the central laboratory.

CONFIDENTIAL

No use, disclosure, or reproduction outside of Omersa without prior written authorization

Table 2: Laboratory Analytes

Comprehensive Metabolic Panel	Complete Blood Count with Differential	Urinalysis	Other Analytes
Albumin	WBC	Specific Gravity	PK
Blood urea nitrogen	RBC	pH	PD
Calcium	Hemoglobin	Protein	ADA
Carbon dioxide (Bicarbonate)	Hematocrit	Glucose	NAB
Chloride	MCV	Ketones	Biomarkers
Creatinine	MCH	Blood (hemoglobin)	24-hour UPE
Glucose	MCHC	Leukocyte esterase	uPCR
Potassium	RDW	Nitrite	uACR
Sodium	Platelet count	Bilirubin	HIV
Total Bilirubin	MPV	Urobilinogen	Hepatitis B
Total Protein	Absolute and percent neutrophils	Reflexive quantitative hematuria test when blood is present	Hepatitis C
ALT	Absolute and percent lymphocytes		Urine pregnancy test ²
Alkaline Phosphatase	Absolute and percent monocytes		Serum pregnancy test ²
AST	Absolute and percent eosinophils		HgbA1c
eGFR ¹	Absolute and percent basophils		

Abbreviations: ADA = anti-drug antibodies; ALT = alanine aminotransferase; AST = aspartate aminotransferase; CMP = comprehensive metabolic panel; eGFR = estimated glomerular filtration rate; HgbA1c = hemoglobin A1c; HIV = human immunodeficiency virus; MCH = mean corpuscular hemoglobin; MCHC = mean corpuscular hemoglobin concentration; MCV = mean corpuscular volume; MPV = mean platelet volume; NAb = neutralizing antibodies; PD = pharmacodynamics; PK = pharmacokinetics; RBC = red blood cells; RDW = red cell distribution width; uACR = urine albumin creatinine ratio; uPCR = urine protein creatinine ratio; UPE = urine protein excretion; WBC = white blood cells

1. eGFR will be calculated by the central laboratory

2. Pregnancy test for women of childbearing potential only. Test must be via serum for the final Run-In Visit and via urine for all other required visits.

10.1.9.1. 24-hour Urine Collection

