10.2.6.2. Follow-Up Visit 2 (FU2) (Weeks 72) ± 14 days

Follow-Up Visit 2 (Weeks 72) must occur within ± 14 days of the respective target dates. The procedures listed below will be performed and documented for each visit:

- Perform symptom-directed physical examination
- Collect vital signs including BP, pulse rate, RR, and temperature (all after at least 5 minutes in a seated position)
- Collect urine sample for UA, uPCR, uACR, and pregnancy
- Complete urine pregnancy test
- Collect blood samples for CMP and CBC+diff
- Assess AEs
- Assess concomitant medications/therapies
- Confirm and document ongoing use of medically acceptable birth control method for patients of childbearing or reproductive potential
- Confirm and document stability of RAS blockade

CONFIDENTIAL

No use, disclosure, or reproduction outside of Omertos without prior written authorization

The procedures below will be performed and documented prior to, during, or after Follow-Up Visit 2:

- Dispense 24-hour urine collection supplies along with collection instructions to patient
 - At site discretion and for the convenience of the patient, these may be dispensed to the patient at any time during the Follow-Up Period. The 24-hour urine collection supplies may be mailed to the patient at any point deemed convenient by the site and patient as long as the supplies are provided in time for the patient to collect the 24-hour urine sample within the required timeframe. Patients will have the option to collect the 24-hour urine specimen within 48 hours prior to Follow-Up Visit 2 or within 48 hours after Follow-Up Visit 2. Patients should be instructed to return the 24-hour urine specimen to the site as soon as possible after its collection. The 24-hour urine collection specimens may be delivered to the study site by the specialty courier service selected by the sponsor, provided the patient has granted consent.
- Collect 24-hour urine sample from patient
- Collect aliquot of urine from 24-hour urine sample to be used for UPE, uPCR and uACR assessment
- Once all laboratory results are available, assess the response and the need for patient study drug retreatment as per Section 10.2.7

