10.2.8. Open-Label Option for High-Risk Patients

Patients with 24-hour UPE > 2 g at baseline will be allowed to receive 12-weeks of open-label active drug (narsoplimab) at Week 72 (18 months post randomization) per protocol, provided they meet the conditions stipulated below:

- Patient has $< 30\%$ reduction in UPE at the OL assessment visit when compared to baseline UPE, and
- Proteinuria is ≥ 3.0 g/day 72 weeks post randomization, as confirmed by two measurements at least 2 weeks apart (but no more than 3 weeks apart), and
- Patient has worsening renal function, defined as a decline in eGFR of > 5 mL/min/m² from baseline.

The Investigator is encouraged to contact the Omeros Medical Monitor to discuss the use of open-label treatment. Open-label treatment with narsoplimab will be administered IV once weekly for 12 weeks. Patients who receive treatment with open-label narsoplimab should continue to attend all study visits and complete all required study procedures. Neither the Investigator nor the patient who receives open-label treatment will be unblinded to the patient's original treatment assignment. Following the 12 weeks of open-label treatment, patients with 24-hour UPE > 1 g/day can receive 6 additional weeks of open-label treatment with narsoplimab (open-label extended treatment) as described in Section [10.2.8.2](#)

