10.2.8.1.4. Open-Label Treatment Visit 12 (OLT12) ± 3 days

For OLT12, the procedures listed below will be performed and documented prior to treatment with narsoplimab:

- Perform complete physical examination including height and weight. Examination of breast, rectal, and genitourinary systems may be deferred unless clinically necessary
- Collect vital signs including BP, pulse rate, RR, and temperature (all after at least 5 minutes in a seated position) prior to dosing
- Complete pre-dose ECG after patient has been supine for at least 5 minutes
- Collect urine sample for uPCR, uACR, UA, pregnancy test, and biomarkers (if consent granted by patient for evaluation of optional research biomarkers, aliquot the urine sample as per instructions in the Lab Manual)
- Complete pregnancy test
- Collect blood samples for CMP, CBC+diff, PK, PD, ADA, NAb, and biomarkers (if consent granted by patient for evaluation of optional research biomarkers, collect additional blood samples)
- Assess AEs
- Assess concomitant medications/therapies
- Confirm and document ongoing use of medically acceptable birth control method for patients of childbearing or reproductive potential
- Confirm and document stability of RAS blockade

Narsoplimab should be prepared and infused per Section [9.4](#).

During OLT12, the procedures listed below will be performed and documented following treatment with narsoplimab:

- Complete post-dose ECG at the end of the narsoplimab infusion after at least 5 minutes of rest in a supine position
- Collect vital signs approximately 5 minutes after the end of the narsoplimab infusion and 30 minutes (± 5 minutes) after the end of the narsoplimab infusion

The procedures listed below will be performed and documented prior to, during or after OLT12:

- Dispense 24-hour urine collection supplies along with collection instructions to patient
 - At site discretion and for the convenience of the patient, these may be dispensed to the patient at any time during the 12-Week Open-Label Treatment Period. Patients will have the option to collect the 24-hour urine specimen within 48 hours prior to OLT12 or within 48 hours after OLT12. Patients should be instructed to return the 24-hour urine specimen to the site as soon as possible after its collection

CONFIDENTIAL

No use, disclosure, or reproduction outside of Omertos without prior written authorization

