## 2.6. Study Endpoint Baseline

When required for the statistical analysis of a variable, the baseline value will be the last recorded value prior to randomization. The exceptions are the baseline 24-hour UPE, 24-hour uPCR, and 24-hour uACR, which are defined as the average of the two respective pre-dose values collected during the last two weeks of the Run-In Period before randomization.

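### The SAP gives the open-label period no baseline of its own, so its eGFR and creatinine change tables carry loss from before the first open-label dose

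*SAP*

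**What the plan says.** SAP 2.6 has one general rule: "the baseline value will be the last recorded value prior to randomization". Its only exceptions are 24-hour UPE, uPCR and uACR, which average two values that are also taken before randomization. Protocol 14.1.6 states the same rule.

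SAP 3.4 summarizes safety separately for the blinded and open-label periods. For laboratory data, SAP 3.4.2 adds actual values and says that "the change from baseline will be tabulated for laboratory results by treatment period (blinded and open-label), treatment group and scheduled visit". It continues: "Shift tables comparing the baseline NCI CTCAE grade to the worst post-baseline grade will be provided by treatment period and treatment group". Neither sentence names a reference value for the open-label period.

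Adverse events are handled differently. Under SAP 3.4.1 an open-label event is treatment-emergent if it first occurs or "worsens in severity from the end of the blinded treatment period after the first dose of narsoplimab in the open-label treatment period".

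One open-label entry condition in Protocol 10.2.8 is "Patient has worsening renal function, defined as a decline in eGFR of" more than 5 mL/min from baseline; SAP 1.2 repeats it. Protocol 10.1.9, Table 2, lists creatinine and eGFR in the metabolic panel, and its footnote says "eGFR will be calculated by the central laboratory". Both therefore fall under SAP 3.4.2.

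**The concern.** A table headed as the open-label period will normally be read as what happened on open-label drug. With the pre-randomization reference, the eGFR and creatinine rows instead show change since study start, in patients admitted because their eGFR had already fallen from that value. In the placebo group the earlier part of that change came before any exposure to narsoplimab.

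The same holds for the shift tables. Any analyte whose CTCAE grade rose in the blinded period and then stayed constant appears again as an open-label shift. The documents do not say that eGFR itself is graded.

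Few open-label values exist to correct the impression. In the open-label visits a metabolic panel is drawn only at OLT12 (Protocol 10.2.8.1.4: "Collect blood samples for CMP, CBC+diff, PK, PD, ADA, NAb, and biomarkers"). None is drawn in the open-label extension (Protocol 20.2.7), and the next is at Week 96. What is at stake is how a descriptive safety table reads, not a test result.

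**Working it through.** The plan gives no figure to reproduce here. The check has two parts.

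**1. What follows from the text alone.** SAP 2.6 fixes the baseline. SAP 3.4.2 uses change from baseline in the open-label period without another definition. Protocol 10.2.8 admits a patient only if the measured eGFR is more than 5 mL/min below baseline. So every eligible patient enters the open-label period with a measured change below -5 on the scale that the table uses. This needs no model.

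**2. Illustration of size.** Inputs:
- Mean slope -5.44 mL/min per year (Protocol 14.1.2; SAP 1.3.2).
- Residual variance 6.5077² = 42.35 (same places; also SAP Appendix 3).
- Monthly slope SD s. The printed figures conflict. Protocol 14.1.2 gives 6.4932² annually and 0.7356² monthly, but 6.4932/12 = 0.5411. SAP Appendix 3 passes 0.5411 as a variance, and √0.5411 = 0.7356. For all patients, 7.8469/12 = 0.6539 is a straight SD conversion. Both s = 0.5411 and s = 0.7356 are therefore run.
- Assumptions: Week 72 = 16.56 months; independent residuals at each visit; only the eGFR entry criterion applied; UPE criteria not modelled; no drug effect; OLT12 at about Week 86 (two UPEs 2 to 3 weeks apart, first dose within 7 days of results, then 11 weeks).

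Formulas: m = -5.44/12 × 16.56 = -7.51; V = s² × 16.56²; D = √(V + 2 × 42.35); a = (-5 - m)/D; r = φ(a)/Φ(a). Among patients with a measured Week 72 change below -5:
- mean measured change = m - D·r
- mean true change = m - (V/D)·r
- mean baseline residual b = (42.35/D)·r
- later change from study baseline = true change at that time - b

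| Quantity (mL/min) | s = 0.5411 | s = 0.7356 |
|---|---|---|
| V; D | 80.3; 12.85 | 148.4; 15.27 |
| a; r | 0.195; 0.678 | 0.164; 0.696 |
| Mean measured change, Week 72 | -16.2 | -18.1 |
| Mean true change, Week 72 | -11.7 | -14.3 |
| b | 2.2 | 1.9 |
| Flat after Week 72: from study baseline | -14.0 | -16.2 |
| Flat after Week 72: from Week 72 value | +2.2 | +1.9 |
| Slope continues, Week 86: from study baseline | -16.3 | -19.0 |
| Slope continues, Week 86: from Week 72 value | about 0 | -0.8 |
| True change, Week 72 to 86 (true × 14/72) | -2.3 | -2.8 |

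For example, with s = 0.7356 and a flat course: -14.3 - 1.9 = -16.2 from study baseline, and -16.2 - (-18.1) = +1.9 from Week 72.

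At Week 96 with continuing slopes, the study-baseline view gives about -18 to -21, against -1.7 to -2.8 from Week 72.

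The Week 72 reference has its own bias. Selection on a low measured value makes later values look about 2 mL/min better than the true course. Neither view is enough alone.

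**The case against.** **The reference is unstated, not wrongly stated.** SAP 3.4.2 names no baseline, SAP 2.6 is headed as the endpoint baseline, and the protocol uses period-specific baselines elsewhere: screening values for the Run-In Period (10.2.1) and final Run-In values for the Initial Treatment Period (10.2.2.2, 10.2.2.4). A programmer might extend that pattern. But none of those passages reaches the open-label period, and the one general rule does. It is still fair to call this a default and not a deliberate choice.

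**Other outputs cover part of the ground.** Actual values are tabulated by period and visit. Laboratory changes that the investigator judges clinically significant are reported as adverse events (Protocol 12.1), and open-label events are counted from the end of the blinded period. This stands and lowers the severity. It does not supply within-patient change from the open-label start, which no planned table gives.

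**Study baseline is a legitimate view.** It shows cumulative change and matches the blinded tables, while the alternative carries regression to the mean. This also stands, and is why both views are needed.

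**Stronger readings.** A reader might infer that renal harm on open-label drug would go undetected; the adverse event route and the actual values do not support that. A reader might also quote the share of patients shown with a decline above 5 mL/min under each reference, but SAP 3.1 plans only n, mean, SD, median and range for continuous variables, so no such percentage would appear.

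**Conclusion.** The point holds as a minor gap that is cheap to close. The certain part is that, as written, the open-label eGFR and creatinine change tables start from a value that every eligible patient had already fallen below by more than 5 mL/min, as measured at eligibility. The SAP re-references open-label adverse events but not laboratory data.

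The larger figures are illustrative. Means of about -14 to -19 mL/min from study baseline, against roughly +2 to -1 from the Week 72 value, rest on registry slopes, the eGFR criterion alone, no drug effect, an assumed Week 86 for OLT12, and a slope SD that the documents print inconsistently. The UPE criteria also select who enters, and could move these means either way.

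A reader might take this to touch the trial's conclusions. It does not: SAP 2.9.4 makes all safety analyses descriptive, and efficacy, alpha and power are unaffected.

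**What to change.** In SAP 2.6, add an open-label baseline: the last value on or before the first open-label dose. For chemistry this is the Week 72 or eligibility sample; Protocol 10.2.6.2 already requires sites to "Collect blood samples for CMP and CBC+diff" at Week 72, and OLT1 has no metabolic panel (Protocol 10.2.8.1.1 and 20.2.6).

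In SAP 3.4.2, present open-label laboratory change and shift summaries from that baseline beside the study-baseline view, for both randomized groups, with each table labelled by its reference. Add a footnote that selecting patients on a low eligibility eGFR brings some upward regression to the mean, without stating a figure.

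Applying the same flag to vital signs and ECG (SAP 3.4.3 and 3.4.4, using OLT1 pre-dose values) is optional, for consistency; entry does not select on those measures.

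Cost: one sentence in SAP 2.6, a matching line in 3.4.2, a second baseline flag, one footnote and one extra set of tables. No new data are needed. The downside is that the new reference carries some regression to the mean, so the study-baseline view should stay.
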